12.2.6	Confidentiality .....	43
12.2.7	Data Protection .....	43
13	STUDY CONDUCT RESPONSIBILITIES .....	44
13.1	PROTOCOL AMENDMENTS .....	44
13.2	MANAGEMENT OF PROTOCOL NON COMPLIANCE .....	44
13.3	SERIOUS BREACH REQUIREMENTS .....	44
13.4	STUDY RECORD RETENTION .....	44
13.5	END OF STUDY .....	44
13.6	CONTINUATION OF TREATMENT FOLLOWING THE END OF STUDY .....	45
13.7	INSURANCE AND INDEMNITY .....	45
14	REPORTING, PUBLICATIONS AND NOTIFICATION OF RESULTS .....	45
14.1	AUTHORSHIP POLICY .....	45
15	REFERENCES .....	46

Title	
Hypoglycaemia	
Precis	A pilot study of 8 months at home, closed loop + low carbohydrate diet (LCD) vs control.
Device	Tandem t:slim X2 with Control IQ and Dexcom G6 system.
Objectives	This study aims to look at the glucagon response to hypoglycaemia in 24 participants with T1D to ascertain if maximising time in range improves glucagon response to insulin-induced hypoglycaemia.
Study Design	Randomised clinical feasibility trial with a 1:1 randomisation to Control IQ + LCD and routine care. 3-month study extension phase for routine care group where they are converted to Control IQ technology.
End Point	To assess if maximising TIR can restore glucagon secretions in T1D.
Population	Adults with c-peptide negative T1D
Sample Size	24 participants
Treatment Groups	Control- Group 1: Standard diabetes care with x3 20 day periods of blinded Dexcom G6 CGM. 3-month study extension where converted to Tandem t:slim X2 with Control IQ technology and Dexcom CGM. Quality of life questionnaires completed at the end of this period and glucose data collected from the CGM. Intervention- Group 2: Tandem t:slim X2 with Control IQ technology and Dexcom G6 CGM + LCD
Participant Duration	9 months + 3 month optional study extension for standard care group
Protocol Synopsis	
After consent eligibility will be assessed. The trial will consist of 3 phases:
 
Phase 1: Baseline data. All participants will complete 20 days of blinded CGM with Dexcom G6
 
Phase 2: Study Run in. Group 2 will have 2 weeks using the t:slim X2 pump with Control IQ technology and the Dexcom G6 CGM unblinded.
 
Phase 3: Study. 8 months. Group 1 will continue routine care as pre-study. They will undergo two periods of blinded Dexcom G6 CGM monitoring each lasting 20 days. Group 2 will continue on their allocated devices and LCD with close monitoring by the study team to ensure TIR is maximised. Both groups will undergo a hyperinsulinaemic hypoglycaemic clamp study at 0 and 8 months. Group 1 will be invited to take part in a 3 month study extension phase where they are converted to the study devices and complete quality of life questionnaires.

## LIST OF ABBREVIATIONS

ACCORD	Academic and Clinical Central Office for Research & Development - Joint office for The University of Edinburgh and Lothian Health Board
AID	Automated insulin delivery
BMI	Body mass index
BSA	Body surface area
CGM	Continuous glucose monitor
CRF	Clinical research facility
CTIMP	Clinical trial of investigational medical product
T1D	Type 1 Diabetes
DAFNE	Dose Adjustment for Normal Eating- A course for adult's with Type 1 Diabetes to help adjusting insulin doses
iDCL	International Diabetes Closed Loop Trial
DKA	Diabetic Ketoacidosis
DPP- 4 Inhibitors	Dipeptidyl peptidase 4 inhibitors
EDTA	Ethylenediaminetetraacetic Acid- a chemical used in blood collection tubes
EGP	Endogenous glucose production
ERI	Edinburgh Royal Infirmary
ERICRF	Edinburgh Royal Infirmary Clinical Research Facility
GCP	Good Clinical Practice
GLP-1	Glucagon-like peptide 1
HbA1c	Glycated Haemoglobin
ICH	International Conference on Harmonisation
ISF	Insulin sensitivity factor- how 1 unit of insulin lowers the blood glucose by
LCD	Low carbohydrate diet
NEJM	New England Journal of Medicine
QA	Quality assurance
QoL	Quality of Life
RCT	Randomised controlled trial
REC	Research Ethics Committee
SCI-Diabetes	Electronic patient record used Scotland-wide for people with diabetes
SSRI	Selective serotonin reuptake inhibitor
TIR	Time in range
USB	Universal serial bus

## 1 INTRODUCTION

### 1.1 BACKGROUND

Glucagon, the pancreatic islet alpha cell product, is a sensitive regulator of glucose homeostasis. In vivo in humans it is critical to the counter-regulatory response to hypoglycaemia (1-3). Almost all people who have had Type 1 diabetes (T1D) for 5 years develop a specific defect in alpha cell Glucagon secretion (4). This defect therefore increases the risk of severe hypoglycaemia. Glucagon secretion may also be inappropriately high in response to hyperglycaemia, meaning that the response is not just absent but is dysregulated.

It is not currently known if preserving glycaemic time in range in T1D leads to improved regulation of glucagon response to hypoglycaemia. Data from longitudinal studies shows that C-peptide (a widely used measure of pancreatic beta cell function) can be preserved in people with optimised TIR, this supports the potential argument that glucagon response to hypoglycaemia may also be preserved with this strategy.

Little is known of the aetiology of this defect, however in a mouse model of neonatal diabetes it was shown that chronic hyperglycaemia leads to a profound change in islet morphology and function without a change in islet number or density (5). Structural and electrophysiological changes in beta cells were shown and attributed to chronic hyperglycaemia. In a later study the same group showed that profound metabolic changes, including significant glycogen accumulation, contributed to the insulin secretory defect of the beta cells (6). Interestingly, in both studies, reducing glucose levels led to the restoration of normal glucose homeostasis and a reversal of the morphological changes of the beta cell.

Although no dynamic assessment of alpha cell function was made the near normalization of glucose homeostasis suggests restoration of both alpha and beta cell function.

Glucagon is a counter-regulatory hormone which helps raise blood glucose levels and it plays a significant role in rescuing people from hypoglycaemia. It is therefore important to understand if this hormonal response, if lost, can be re-established in people with Type 1 Diabetes.

This pilot study aims to look at the Glucagon response to hypoglycaemia in 24 patients with T1D to ascertain whether maximizing blood glycaemic time-in-range (TIR) improves the Glucagon response to hypoglycemia.

Continuous Glucose Monitoring systems (CGMs) have made it possible to quantify glycaemic time in range (TIR), defined as blood glucose  $>70$  and  $<180$  mg/dl ( $>3.9$  and  $<10.0$  mmol/L) (7), this has greatly expanded the understanding of glycaemic control beyond HbA1c alone. Maximising TIR is emerging as a major goal of treatment in T1D (8).

We aim to improve TIR by using an AID system, the t:slim X2 insulin pump with Control IQ technology, and the Dexcom G6 CGM in conjunction with a low carbohydrate diet. We are introducing a low carbohydrate diet as postprandial hyperglycaemia contributes significantly to overall glycaemic burden. Data from the Type 1 Diabetes Exchange indicate that  $< 30\%$  of patients achieve glycaemic targets (8).

### 1. Automated Insulin Delivery systems, AIDs

Automated insulin delivery systems (AIDs) have been shown to improve TIR in both the paediatric and adult population (9, 10). This technology combines an insulin pump, a CGM system and an algorithm allowing automatic adjustment of insulin delivery based on a patient's blood glucose.

We propose using the Dexcom G6 CGM and the Tandem t:slim X2 insulin pump. The Tandem t:slim X2 has built in Control IQ technology, an algorithm that utilises CGM data to adjust insulin delivery (Tandem Diabetes Care, San Diego, US) (11).

The features available with this system are:

- Automated insulin correction boluses administered using CGM data.
- A dedicated hypoglycaemia safety system that attenuates smoothly, or discontinues, insulin delivery using CGM and insulin-on-board information.
- Gradually intensified control overnight. During the day the system targets a range of 112.5-160 mg/dl (6.2-8.9 mmol/l). It is more aggressive at night – the goal is to arrive at 112.5-120 mg/dl (6.2-6.7mmol/l) by the time the user wakes up.
- Control-IQ also has an “exercise mode” that changes the target to be closer to 140-160 mg/dl (7.8-8.8 mmol/l).

### AIDs, using Control IQ and Dexcom G6, trial results.

Positive clinical results from studies of the Tandem t:slim X2 insulin pump with Control-IQ advanced hybrid closed-loop technology have been reported. Data demonstrated that the system achieved the primary outcome of increasing TIR without any severe hypoglycaemic events.

The iDCL study published in June 2019 (12) showed TIR for participants using Control-IQ technology for 6 months was 71% per day compared to 59% per day for participants in the control group (using sensor augmented pump therapy, i.e. open loop.). During the overnight period time in range with Control-IQ technology was 76 % compared to

59% in the control group. Time spent with glucose values above 180 mg/dL (10.0 mmol/l) was 27% in those using Control-IQ technology compared to 39% in the control group. Time spent below 70 mg/dL (3.9 mmol/l) was 1.4 % with Control-IQ technology compared to 1.9% in the control group and time spent below 54 mg/dL (3.0 mmol/l) was 0.21 % compared to 0.24 % in the control group.

Protocol 3 of the iDCL study was released in the NEJM in October 2019 (11). This showed that the TIR in the closed-loop group increased from  $61\pm17\%$  at baseline to  $71\pm12\%$  during the 6 months trial period and remained unchanged at  $59\pm14\%$  in the control group. The results with regard to the main secondary outcomes (percentage of time that the glucose level was  $>180\text{mg/dl}$  (  $10.0\text{ mmol/l}$ ) mean glucose level, HbA1c, and percentage of time that the glucose level was  $<70\text{ mg/dl}$  (  $3.9\text{ mmol/l}$ ) or  $<54\text{ mg/dl}$  (  $3.0\text{ mmol/l}$ ) all favoured the closed-loop system. These results were demonstrated in people with and without prior experience with insulin pump therapy. In addition to time in range those using Control-IQ technology also saw statistically significant improvements in HbA1c and reductions in mean glucose. This is the most impressive data on AIDs to date.

## 2. Low Carbohydrate Diet

Maximising TIR using an AID system as described will allow us to test the hypothesis that chronic hyperglycemia *per se* plays a causative role in the development of defective glucagon secretion in T1D. However, it remains possible that the AID system may be insufficient given that post-prandial hyperglycemia still remains difficult to fully control with these devices (13).

One additional approach that may address post-prandial hyperglycemia effectively is a Low Carbohydrate Diet (LCD), defined as  $<130\text{g}$  per day of carbohydrates or 25% carbohydrates as a proportion of calories. No randomized controlled trials (RCTs) exist in this field in T1D but small observational surveys confirm the safety and efficacy of controlling post-prandial hyperglycemia in adults with T1D using a low or very low carbohydrate diet (14).

In this study we propose a carbohydrate portion of 30-40g carbohydrate per meal. This will be initiated by experienced healthcare professionals in this field. Patients will receive education about this diet at baseline. The ERICRF routinely uses this diet for post islet transplant patients.

We will ensure patient safety in this arm of the trial by monitoring blood ketones daily and will supply the meters and test strips for this.

We will supply nutritional scales to assist with carbohydrate counting and provide support and advice on this throughout the trial.

## 1.2 RATIONALE FOR STUDY

It is not currently known if maximizing TIR by principally reducing the exposure of the alpha cell to hyperglycemia is sufficient to restore glucagon secretory responses to insulin-induced hypoglycaemia in people with T1D.

We will attempt to answer this question by maximizing glycaemic TIR using new-generation AIDs in combination with a LCD. In addition, participants will be intensively followed up by study investigators to achieve maximal glycaemic TIR.

This will provide proof-of-principle that restoration of the glucagon response to insulin induced hypoglycaemia is possible in T1D. If these findings are confirmed this study will drive efforts to restore the glucagon response to hypoglycaemia not only by optimising glycaemic TIR but also by other pharmacological measures. It will also drive researchers to investigate if there are compositional, structural and, or, functional changes in the islet after regulation of the glucagon response.

Most importantly however is the impact on patients and patient care. In the short and the long-term restoration of this response would significantly reduce morbidity and mortality from hypoglycaemia impacting on quality-of-life for the patient as well as having significant socio-economic implications.

## 2 STUDY OBJECTIVES

### 2.1 OBJECTIVES

#### 2.1.1 Primary Objective

Does maximizing TIR using AIDs with a LCD restore the glucagon response to insulin-induced hypoglycaemic in people with type 1 diabetes.

#### 2.1.2 Secondary Objectives

- Has the quality of life (QoL) improved with improved blood sugar control?
- Are there fewer hypoglycaemic episodes?
- Is there a lower burden of diabetes care?
- Has the fear of Hypoglycaemia changed as a result of using this technology?
- Has satisfaction with their diabetes treatment improved as a result of using this technology?
- Is there an improvement in HbA1c using this technology?
- Endogenous glucose production and glycerol kinetics as measured by stable isotope studies (glycerol isotope will be used when supply is available)
- Is there a similar improvement in TIR between participants using the HCL system and following a LCD and those using the HCL system and following their pre-study diet

- Is there a difference in QoL between participants using the HCL system and following a LCD and those using the HCL system and following their pre-study diet

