### 2.2.2 Secondary Endpoints

Treatment satisfaction, fear of hypoglycaemia and quality of life at baseline compared to endpoint using validated questionnaires. Changes in endogenous glucose production and glycerol kinetics as measured by stable isotope studies. The difference in time in range and QoL between participants using the HCL system and following the LCD and those using the HCL system alone will be compared.

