## 4 STUDY POPULATION

### 4.1 NUMBER OF PARTICIPANTS

Enrolment will proceed with the goal of having 24 participants enter the trial. The participants will be people with type 1 diabetes recruited from the NHS Lothian diabetes pump waiting list and type 1 diabetes clinic. Recruitment will be staggered with each participant entering the trial for a 9 month period. The trial is expected to last 14 months.

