#### Randomisation

We will perform stratified random sampling according to age, gender and BMI. We will then provide envelopes to randomly assign final members from the various strata,

these envelopes will be kept in a secure, locked unit within in the clinical research facility. This technique ensures that observations from all relevant strata are included in the sample. by stratified sampling to match for: age, gender and BMI. They will be assigned to one of two groups:

- Group 1: Controls: standard diabetes care with blinded CGM (Dexcom G6) on three occasions lasting 20 days. All will be invited to a 3-month study extension phase where they will be converted to the study devices.
- Group 2: New-generation AIDs (t:slim X2 insulin pump with Control-IQ technology) with CGM (Dexcom G6) and a low carbohydrate diet (30-40g of carbohydrate per main meal portion). They will also have a 20-day period of blinded CGM (Dexcom G6) at baseline

Amendment: 28/09/22: Recruitment and retention to group 1 has been challenging with potential participants not wanting to engage with the study if allocated to group 1. This has led to unbalanced study groups. Currently there are 11 participants in group 2 and only 3 participants in group 1 (with a further 2 participants previously recruited but choosing to leave the study early). In order to balance groups from now on participants will be approached to take part in the study and informed up-front that they will be allocated to group 1.

Dexcom G6 clinical supplies, technical and software assistance will all be provided by Dexcom (see letter of support: Dr [name], Senior US Medical Director, Dexcom).

Participants will be asked to choose an envelope at random at the end of the screening visit which will allocate them to a group. At this time arrangements for subsequent visits will be made. We will send those randomised to group 2 training materials for the insulin pump and CGM. Participants will be allocated to a group within 1 week of the screening visit. This will change in version 8 of the protocol (28/09/22), from this point participants will only be recruited to the control group (group 1) and not randomised.

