### Monitoring Period

#### **Group 1**

Group 1 will continue on their standard diabetes care. At 4 months they will perform a 20 day period of blinded CGM monitoring. This will require them to insert the CGM device on two occasions during this 20 day period. During this 20 day period this group will continue on their standard diabetes care, including monitoring their own blood glucose, as they will not be able to view the data from the CGM device. Participants in this group will perform a further 20 day period of blinded CGM monitoring prior to the second hypoglycaemic clamp study. This means that participants in this group will have to insert the CGM device on 6 occasions during the study period. In each of these periods of blinded CGM monitoring the aim will be to collect at least 14 days of data. Study staff will collect the CGM devices at the end of each 20 day blinded period so that the data can be downloaded for analysis. CGM devices for these two blinded periods will be delivered to the participants' home. The device for the 4 month period will then be collected from the participant by study staff. The device used prior to the second clamp study can be given to study staff at the clamp study visit. During each of these blinded CGM periods participants will be asked to complete a 7-day food diary, to include 5 week days and 2 weekend days. This can be in the form of a paper diary provided by study staff or a mobile phone application. This can be returned to study staff at the next visit or by post, a stamped addressed envelope will be provided. After the second clamp study participants will be invited to take part in a 3-month study extension phase. During this time they will be converted to the study devices. They will be asked to upload their study pump once a week and will have ad hoc contact with the investigators over this time to adjust pump settings as required. At the end of the 3 months they will be sent quality of life questionnaires to complete along with a stamped addressed envelope to return these to the investigators.

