## 9.2 PROPOSED ANALYSES

In primary analyses, the glucagon response to insulin induced hypoglycaemia at 0 and 8 months will be compared to the individual's baseline glucagon responses within each group. In further exploratory analyses, the participants in the highest tertile of glycaemic TIR as a group over the 8 months will be compared to those in the lowest tertile over the 8 months as a

group. The rate of appearance (Ra) of the stable isotopes will be used as a marker of endogenous glucose production. Analysis of tracee:tracer ratio will be made by mass spectrometry. The TIR of participants completing the study 3-month extensions will be compared to that of group 2 during the study.

We predict minimizing exposure of alpha cells to hyperglycemia with AID +/- VLCD should significantly enhance glucagon.

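### Closed loop with v without the diet: 9.2 compares extension completers with Group 2 without baseline TIR or matched periods, and at about 11 v 11 a null result would not support similarity

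*Combined protocol and SAP*

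**What the plan says.** The comparison of closed loop with and without the low-carbohydrate diet appears in three places, worded differently each time.

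- Section 2.1.2 (Secondary Objectives): "Is there a similar improvement in TIR between participants using the HCL system and following a LCD and those using the HCL system" while keeping their pre-study diet. This is a question about similarity, and about improvement.
- Section 2.2.2 (Secondary Endpoints): "The difference in time in range and QoL between participants using the HCL system and following the LCD and those using the HCL system alone". This is a question about a difference, with no mention of improvement.
- Section 9.2 (Proposed Analyses): "The TIR of participants completing the study 3-month extensions will be compared to that of group 2 during the study". No baseline, interval, test, margin or matched period is given.

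The data for a baseline-adjusted comparison are already planned. Everyone wears a blinded sensor for 20 days at Visit 2. Of Group 1, section 6.1 (Monitoring Period) adds: "Participants in this group will perform a further 20 day period of blinded CGM monitoring prior to the second hypoglycaemic clamp study". The extension follows that clamp.

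On numbers, section 4.1 states: "Enrolment will proceed with the goal of having 24 participants enter the trial". The 28/09/22 amendment under Randomisation reports: "Currently there are 11 participants in group 2 and only 3 participants in group 1". It adds that 2 earlier Group 1 recruits had already left. From version 8, new participants enter Group 1 only and are not randomised. The synopsis describes the extension as optional.

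**The concern.** An objective about improvement needs each person's TIR before closed loop. Section 9.2 names none, so a difference in starting TIR between the groups would be counted as an effect of the diet or would hide one. Randomisation would normally limit that risk. Here most of Group 1 may be recruited without it.

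Three further features weaken the comparison:

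- Read literally, only those who complete the extension count in Group 1, and no such condition is set for Group 2.
- Three months on closed loop are set against the 8-month study period.
- Staff contact differs: ad hoc in the extension, daily sensor review in Group 2.

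Finally, similarity cannot be inferred from the absence of a difference when the interval is wide. What is at stake is whether a reader is told that the diet adds nothing to closed loop when the data could not exclude a large contribution.

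**Working it through.** **Plan's own figure.** Section 9.1 justifies 24 participants by the size of an earlier study. It gives no alpha, power, SD, effect or margin, so there is no calculation to reproduce.

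**Inputs**

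| Input | Value | Source |
|---|---|---|
| Total entering | 24 | Section 4.1 |
| At the amendment | Group 2: 11; Group 1: 3, plus 2 leavers | Randomisation |
| SD of TIR on closed loop | 12 points | Section 1.1, 6-month trial (71 ± 12%) |
| Whole closed-loop effect | 71 − 61 = 10 points, or 71 − 59 = 12 points | Section 1.1 |
| Correlation of baseline with closed-loop TIR | 0.5 to 0.7 | Assumption |

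The 12-point yardstick is the report that "TIR for participants using Control-IQ technology for 6 months was 71% per day compared to 59% per day" in the control group. The 10-point yardstick is the change within the closed-loop arm.

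**Group sizes (inferred, not printed).** Entered so far: 11 + 3 + 2 = 16. Places left: 24 − 16 = 8, all in Group 1. Group 1 then has 3 + 8 = 11, giving 11 v 11. If the 2 leavers are replaced it is 13 v 11. If some decline or leave the extension it is fewer; 8 v 11 is used as an example.

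**Unadjusted 95% CI half-width** = t(0.975, n1 + n2 − 2) × SD × √(1/n1 + 1/n2)

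- 11 v 11: 2.086 × 12 × √(2/11) = 2.086 × 5.12 = 10.7 points
- 8 v 11: 2.110 × 5.58 = 11.8 points
- 13 v 11: 2.074 × 4.92 = 10.2 points

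At 11 v 11, other assumed SDs give 7.1 (SD 8), 8.9 (SD 10), 12.5 (SD 14) and 15.1 (SD 17).

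**Power for a diet effect** (two-sided 5%, noncentral t, 11 v 11, SD 12, unadjusted)

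- 5 points: 15%
- 10 points: 46%
- 12 points: 61%

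So a diet effect as large as the closed loop's own would be missed 54% of the time at 10 points and 39% at 12.

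**With baseline adjustment.** Residual SD = 12 × √(1 − r²), which is 10.4 at r = 0.5 and 8.6 at r = 0.7.

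- Half-width, 11 v 11: 2.086 × 10.4 × √(2/11) = 9.2 points; with 8.6, 7.6 points
- Power at 10 points: 57% to 74%
- Power at 12 points: 73% to 88%

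Adjustment helps, and it addresses measured baseline imbalance. Even so, an observed difference of exactly zero would leave diet effects of about 8 to 9 points either way inside the interval.

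**The case against.** The strongest reply is that this is one secondary objective in a 24-person feasibility pilot and leaves the primary endpoint untouched. The objective may use similar in its everyday sense, and the endpoint in 2.2.2 already speaks of a difference. Section 9.2 is brief and does not rule out analysing change. These points are fair: this is under-specification rather than a declared choice to ignore baseline. They do not remove the need to settle the analysis, because 9.2 as it stands names neither baseline nor period, and the three sections do not agree.

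A reader might go further in three ways that the documents do not support.

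- *That a non-significant result is likely even if the diet adds as much as closed loop.* Unadjusted, this holds narrowly at 10 points (power 46%) and fails at 12 (61%). With adjustment, significance is the likelier result at both.
- *That the trial will declare similarity from a non-significant test.* No section names a test for this comparison or says so. The risk is that the plan leaves that reading open.
- *That no margin below about 8 points could ever be met, or that similarity cannot be shown at all.* This depends on SD 12, a correlation of at most 0.7 and a 95% interval. At r = 0.7 the 90% half-width, used in a 5% equivalence test, is 6.3 points. At SD 8, unadjusted, a 10-point margin would have 77% equivalence power if the true difference were zero. That margin, though, is about as large as the whole closed-loop effect.

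It is also fair to say that baseline adjustment leaves the differences in duration and staff contact, and any unmeasured effect of non-random allocation. The fix has to deal with these separately.

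**Conclusion.** The concern holds in this form. The objective, endpoint and analysis ask different questions. As written, the analysis lets baseline TIR differences into the answer, keeps only extension completers in Group 1, and compares unequal periods. The unadjusted 95% half-width of about 10 to 12 points is about the size of the whole closed-loop effect, so a diet effect that large could easily be missed and a null result would not support similarity.

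This rests on the SD of 12 from the cited 6-month trial and on the inferred group sizes; the conclusion is the same at 8, 11 or 13 v 11. The gain from adjustment rests on an assumed correlation of 0.5 to 0.7. The point concerns a secondary objective only, but it should be settled before analysis because doing so costs almost nothing.

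**What to change.** Align sections 2.1.2, 2.2.2 and 9.2 before the data are analysed.

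1. State the aim as estimating the between-group difference in TIR improvement, with a 95% CI. Say that a non-significant difference will not be reported as similar.
2. Analyse closed-loop TIR by ANCOVA on each person's last blinded 20-day window before closed loop: Visit 2 for Group 2, the window before the second clamp for Group 1.
3. Include everyone who starts the extension, using all sensor data uploaded.
4. For Group 2, use the first 3 months on closed loop, counted from the same starting point as in the extension.
5. Label the comparison exploratory and non-randomised, and note that staff contact differed (ad hoc v daily review).

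Cost: wording only, with no new visits, samples or participants. The sponsor gives up a claim of similarity, and Group 2 data after 3 months are not used in this comparison.
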